A Secondary Objective of this study is to evaluate the magnitude of SARS-CoV-2-specific antibody binding and neutralization titers in serum samples. This objective is descriptive in nature and will be accomplished by estimating the geometric mean titer (GMT) at each timepoint when samples are collected.

The precision with which a true GMT can be estimated from observed data depends on the standard deviation (SD) of the measurements, in the logarithmic scale, and the sample size. [Table 5](#) displays two-sided 95% confidence intervals for the GMT for several values of the observed antibody titer.

Table 5: Two-sided 95% confidence intervals based on observing a particular average \log_e -antibody titer in subjects' groups, taking 0% or 20% attrition into consideration (n = 12, 10, 8, 7)

Observed average \log_e antibody titer	SD of \log_e antibody titer	95% confidence interval			
		n=12	n = 10	n = 8	n=7
$\log_e(5)$	0.5	(3.6, 6.9)	(3.5, 7.2)	(3.3, 7.6)	(3.1,7.9)
$\log_e(20)$		(14.6, 27.5)	(14, 28.6)	(13.2, 30.4)	(12.6,31.8)
$\log_e(50)$		(36.4, 68.7)	(35, 71.5)	(32.9, 75.9)	(31.5,79.4)
$\log_e(100)$		(72.8, 137.4)	(69.9, 143)	(65.8, 151.9)	(63,158.8)
$\log_e(250)$		(182, 343.5)	(174.8, 357.5)	(164.6, 379.7)	(157.4,397)
$\log_e(500)$		(363.9, 687)	(349.6, 715)	(329.2, 759.5)	(314.9,794)
$\log_e(1000)$		(727.8, 1373.9)	(699.3, 1430)	(658.4, 1518.9)	(629.8,1587.9)
$\log_e(5)$	1.0	(2.6, 9.4)	(2.4, 10.2)	(2.2, 11.5)	(2,12.6)
$\log_e(20)$		(10.6, 37.8)	(9.8, 40.9)	(8.7, 46.1)	(7.9,50.4)
$\log_e(50)$		(26.5, 94.4)	(24.5, 102.2)	(21.7, 115.4)	(19.8,126.1)
$\log_e(100)$		(53, 188.8)	(48.9, 204.5)	(43.3, 230.7)	(39.7,252.1)
$\log_e(250)$		(132.4, 471.9)	(122.3, 511.2)	(108.4, 576.8)	(99.1,630.4)
$\log_e(500)$		(264.9, 943.9)	(244.5, 1022.5)	(216.7, 1153.6)	(198.3,1260.7)
$\log_e(1000)$		(529.7, 1887.7)	(489, 2044.9)	(433.4, 2307.2)	(396.6,2521.5)

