No formal multiple comparison adjustments will be employed for multiple primary or secondary endpoints. However, multiplicity adjustments will be made for certain primary or secondary endpoint assays, as discussed below, when the assay endpoint is viewed as a collection of hypotheses (e.g., testing multiple pseudo-viruses to determine a positive antiviral functional activity response). Unless otherwise noted, 95% confidence intervals will be calculated. Any statistical tests will be 2-sided and will be considered statistically significant if the p-value is below 0.05.

An SAP will be developed by the SDCC and finalized prior to data lock. Unless specified otherwise in the SAP, missing data will not be imputed.

General Approach

Unless otherwise noted in the SAP, continuous variables will be summarized using the following descriptive statistics: n (non-missing sample size), mean, standard deviation, median, maximum and minimum. The frequency and percentages (based on the non-missing sample size) of

observed levels will be reported for all categorical measures. Unless otherwise specified in the SAP, geometric means of relevant continuous endpoints will be computed as Williams means.

Analysis of the Primary Endpoint(s)

Summaries and analysis of safety data will be presented for the Safety Analysis Population.

Solicited reactogenicity signs and symptoms (local and systemic) will be summarized by severity for each day post study vaccination (Days 1-8) and as the maximum severity over all 7 days.

Additionally, solicited AEs will be analyzed by taking the most severe response over the follow-up period, dichotomizing into a binary variable (none versus mild, moderate, or severe) and using standard techniques, such as exact confidence intervals (CI), to summarize the proportion of subjects reporting each symptom, any application site symptom, and any systemic symptom.

Unsolicited non-serious AEs will be collected from the time of first vaccination through 28 days after each study vaccination. Unsolicited AEs will be coded by MedDRA® for Preferred Term and SOC. All SAEs will be collected from the time of first vaccination through the end of the study. SAEs will be described by detailed listings showing the event description,

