MedDRA® Preferred Term and SOC, relevant dates (vaccinations and AEs), severity, relatedness, and outcome for each event. Non-serious unsolicited AEs will be summarized as number and percentage of subjects reporting at least one event in each MedDRA® Preferred Term and SOC, cross tabulated by severity and relationship to study product. Additionally, the proportion of subjects and exact 95% CIs of AEs in aggregate and by MedDRA® categories will be computed.

Clinical laboratory data will be summarized as change from baseline and by severity for each visit, and as the maximum over all post study vaccination visits.

Analysis of the Secondary Endpoint(s)

Antibody titers (binding and neutralizing antibody) will be described by group and timepoint using geometric mean titer (GMT) and geometric fold-rise (GMFR), including 95% confidence intervals based on the t-distribution. Undetectable titers will be imputed as one-half of the lower limit of quantitation and the number and proportion of subjects with undetectable titers at each timepoint will be reported. Plots such as reverse cumulative distributions or longitudinal presentations of GMTs will be presented.

Analysis of ICS endpoints will present the percent of cells expressing various cytokines or combinations of cytokines, including 95% confidence intervals, tabularly and graphically by group, peptide pool/stimulant, and timepoint. ELISpot results will be summarized by cytokine,

group, peptide pool/stimulant, and timepoint using summary statistics and 95% confidence intervals.

Baseline Descriptive Statistics

Summaries of demographic variables such as age, sex, ethnicity, and race will be presented by cohort and overall. Summaries of baseline clinical laboratory values will be presented by cohort and overall.

Tabulation of Individual Subject Data

In general, all data will be listed, sorted by cohort and subject, and when appropriate by visit number within subject.

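### Section 10.5 defaults to Williams means, although the only geometric means it names, GMT and GMFR, contain no zeros; applied to subject-level fold-rises this biases GMFR upward near or below 1

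*Protocol*

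**What the plan says.** Protocol Section 10.5, General Approach, sets a default estimator: "Unless otherwise specified in the SAP, geometric means of relevant continuous endpoints will be computed as Williams means". The formula is not printed, and the SAP that could change the default is not at hand.

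Under Analysis of the Secondary Endpoint(s), the same section describes binding and neutralizing titers by group and timepoint "using geometric mean titer (GMT) and geometric fold-rise (GMFR), including 95% confidence intervals based on the t-distribution". These are the only geometric means it names. It does not say whether GMFR is the geometric mean of individual fold-rises or a ratio of group GMTs.

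For low titers it states: "Undetectable titers will be imputed as one-half of the lower limit of quantitation". No such rule is given for ICS or ELISpot.

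Section 10.2 says that GMT precision "depends on the standard deviation (SD) of the measurements, in the logarithmic scale, and the sample size". Table 5 then gives intervals for SDs of 0.5 and 1.0 of the natural-log titer.

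**The concern.** Adding 1 before taking logs is a device for data that contain zeros, whose logarithm does not exist. After half-LLOQ imputation every titer is positive, and so is every ratio of two titers. For GMT and GMFR the shift therefore solves no problem, yet it changes the estimate.

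The change is negligible when values are large compared with 1. A fold-rise is not: a value of 1 means no change. Adding 1 to a ratio pulls the average upward, by an amount that grows with the spread between subjects. Two groups with the same true GMFR but different spread would then report different values. The estimate also loses two useful properties: it no longer equals the ratio of GMTs in subjects with both samples, and inverting the ratio no longer inverts the answer.

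Section 10.1 rules out hypothesis tests between schedule and dose groups, so estimates and intervals are the immunogenicity result. Section 2.2.4 says the vector, cassette, schedule and dose with the strongest responses will be identified from this trial. Stage 2 subjects are already vaccinated and are followed to Days 181 and 366 (Table 2), where fold-rises near or below 1 are plausible.

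**Working it through.** **Inputs.** Table 5 (Section 10.2): SD of natural-log titer 0.5 and 1.0; n = 12, 10, 8, 7. Assumed: Williams mean W = exp(mean of ln(x+1)) − 1; lognormal values; Table 5's SDs also applied to the log fold-rise, because the protocol gives no SD for fold-rise.

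**1. The plan's own figure.** Table 5 follows GMT × exp(± t(0.975, n−1) × SD/√n). For GMT 100, SD 1.0, n = 10: 2.262 × 1.0/√10 = 0.715 and exp(0.715) = 2.045, giving (48.9, 204.5) as printed. All 56 cells reproduce this way. Planned precision is thus for the ordinary geometric mean, without a shift.

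**2. An exact example.** Two subjects have fold-rises 0.25 and 4.
- Ordinary: √(0.25 × 4) = 1.0.
- Williams: √(1.25 × 5) − 1 = 2.5 − 1 = 1.5.

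**3. Subject-level fold-rises.** For a lognormal fold-rise X, W = exp(E[ln(1+X)]) − 1, evaluated by numerical quadrature:

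| True GMFR | Williams, SD 0.5 | Williams, SD 1.0 |
|---|---|---|
| 0.25 | 0.275 (+10%) | 0.353 (+41%) |
| 0.5 | 0.541 (+8%) | 0.663 (+33%) |
| 1 | 1.062 (+6%) | 1.239 (+24%) |
| 2 | 2.083 (+4%) | 2.326 (+16%) |
| 4 | 4.101 (+2.5%) | 4.413 (+10%) |
| 10 | 10.118 (+1%) | 10.511 (+5%) |

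Hand check: a second-order expansion gives W ≈ (1+g) × exp(½ SD² g/(1+g)²) − 1, with g the true GMFR. At g = 1 and SD 0.5 this is 2 × exp(0.03125) − 1 = 1.063, close to 1.062.

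Non-reciprocity at SD 1.0: W(2) × W(0.5) = 2.326 × 0.663 = 1.54, where an ordinary geometric mean gives 1.

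**4. Intervals.** 100,000 simulated samples per setting, t-interval on ln(1+x), back-transformed, SD 1.0:
- True GMFR 1, n = 12: coverage 93.6%; interval wholly above 1 in 5.0% of samples (nominal 2.5%).
- True GMFR 1, n = 7: coverage 94.9%.
- True GMFR 0.5, n = 10: interval wholly below 1 in 38% of samples, against 50% with the ordinary geometric mean.

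**5. GMFR as a ratio of Williams GMTs.** SD 1.0 at both visits:
- True ratio 1: 1.000.
- True 0.5, baseline GMT 100: 50.609/100.627 = 0.503.
- True 0.5, baseline GMT 5: 2.854/5.439 = 0.525.

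**6. GMT itself.** At SD 0.5 and 1.0: +2.1% and +8.8% at a GMT of 5; +0.6% and +2.8% at 20; +0.13% and +0.63% at 100, and less above that.

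**The case against.** The strongest reply is that the sentence yields to the SAP and covers only endpoints it calls relevant, without naming GMFR. That stands as a limit: whether any reported GMFR would use a Williams mean cannot be known from the protocol. It does not dispose of the point, because this is a chosen default and not a gap. Section 10.5 requires the SAP only before data lock, while Section 10.4.2 allows immunogenicity analyses earlier.

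The bias also needs the default to be applied to subject-level fold-rises. Under the ratio-of-GMTs reading it is small. Section 10.5 permits either reading, which is itself a reason to define GMFR.

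The fold-rise SD is borrowed. At 0.5, a true GMFR of 1 moves only to 1.06. Groups have at most 12 subjects, and the Table 5 interval at n = 10 and SD 1.0 runs from about 0.49 to 2.04 times the estimate, so sampling error is much larger than the bias. The objective is secondary and descriptive.

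Three stronger readings are tempting but not supported:
- A reader might infer that the default would show a rise where there is none. The point estimate shifts, but with a true GMFR of 1 the interval still covers 1 in 93.6% to 94.9% of samples in the SD 1.0 settings shown.
- A reader might infer that an ICS geometric mean would become nearly an arithmetic mean. None is planned: "Analysis of ICS endpoints will present the percent of cells expressing various cytokines or combinations of cytokines, including 95% confidence intervals", while "ELISpot results will be summarized by cytokine" and other factors with summary statistics. Half-LLOQ imputation is stated for titers only, so zeros may remain in these assays and a zero-tolerant mean has a rationale there.
- A reader might infer from the change of scale that Table 5 is wrong. Every cell reproduces, and GMTs of 100 or more are practically unaffected.

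**Conclusion.** The point holds in limited form. As written, Section 10.5 makes Williams means the default for geometric means, although the two it names rest on data without zeros and Section 10.2 plans GMT precision on the unshifted log scale. Applied to subject-level fold-rises, the default overstates GMFR: by 6% to 24% at a true 1.0 and by 8% to 33% at a true 0.5, for log SDs of 0.5 to 1.0. The bias fades as the fold-rise grows.

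This rests on the usual Williams formula, lognormal fold-rises, Table 5's titer SDs carried over to fold-rise, and the SAP leaving the default in place. No sample size or planned precision figure is affected. Severity is low; it is a free improvement.

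**What to change.** In Section 10.5 or the SAP, state that:
- GMT and GMFR are ordinary geometric means, exp(mean of ln), with t-intervals formed on the natural-log scale and back-transformed;
- GMFR is computed from subject-level log fold-rises;
- Williams means are limited to endpoints where true zeros can remain, for example ELISpot or ICS, if a geometric mean is used for them.

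With this change a true GMFR of 1.0 or 0.5 is estimated on its own scale without the shift, GMFR again agrees with the ratio of GMTs in subjects with both samples, and Table 5 stands as printed. The cost is a sentence or two of text and no data. The one downside is that some reported fold-rises become smaller than under the default.

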3.2 Study Objectives and Endpoints

Table 2: Objectives and Endpoints (Outcome Measures)

Objectives	Endpoints (Outcome Measures)
Primary	

 To assess the safety and tolerability of different doses of ChAd-S or ChAd-S-TCE, and SAM-S or SAM-S-TCE when administered as: 
 prime-boost in healthy naïve adult subjects boost in healthy adult subjects previously vaccinated with an EUA/licensed mRNA or adenoviral-vectorized COVID-19 vaccine 	
 Occurrence of solicited local reactogenicity signs and symptoms for 7 days following each study vaccination Occurrence of solicited systemic reactogenicity signs and symptoms for 7 days following each study vaccination Occurrence of unsolicited AEs for 28 days following each study vaccination Change from baseline for clinical safety laboratory parameters 7 days after each study vaccination Occurrence of SAEs and AESIs, including PIMMCs, MAAEs and NOCMCs, throughout the entire study following the first study vaccination
Secondary	

 To assess the humoral immunogenicity of ChAd-S or ChAd-S-TCE, and SAM-S or SAM-S-TCE 	
 Response rate, and magnitude of SARS-CoV-2-specific antibody binding and neutralization titers (including against emergent viral strains, e.g., B.1.1.7) in serum samples will be assessed via a range of assays measuring total Spike-specific IgG (ELISA-based), and function (neutralization, RBD binding, or similar) in serum on the following days:

Objectives	Endpoints (Outcome Measures)
	
For Stage 1, Groups 1 and 3A: Days 1 and 29 post Dose 1; then Days 29, 181, and 366 post Dose 2
 
For Stage 1, Groups 3B and 4: Days 1, 29, 57, and 85-130 post Dose 1; then Days 15, 29, 85, 181, and 366 post Dose 2
 
For Stage 2, Groups 5-7A*, 7B*, 9, 10A, 10B, and 11A, 11B, and 13-15: Days 1, 15, 29, 85, 181, and 366 post study vaccination
 
For Stage 2, Groups 8A*, 8B* and 12A, 12B: Days 1, 15, 29, and 57 post Dose 1; then Days 15, 29, 85, 181, and 366 post Dose 2

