7 DESCRIPTION OF CLINICAL AND LABORATORY EVALUATIONS

7.1 Clinical Evaluations

Complete medical history will be obtained by interviewing the subjects at the first study visit. Subjects will be queried regarding a history of significant medical disorders of the head, eyes, ears, nose, throat, mouth, cardiovascular system, lungs, gastrointestinal tract, liver, pancreas, kidney, urologic system, nervous system, blood, lymph nodes, endocrine system, musculoskeletal system, skin, and genital/reproductive tract. A history of any allergies, clotting or other abnormality of the coagulation system, cancer, immunodeficiency, psychiatric illness, substance abuse, and autoimmune disease will be solicited. At follow-up visits after the first study visit, an interim medical history will be obtained by interview of the subjects noting any changes since the previous clinic visit, phone call, or other form of contact. The interim medical history should include an assessment for new medical conditions and symptoms suggestive of an autoimmune disorder.

Concomitant medications will be collected as described in [Section 7.1.1](#).

At the screening visit (Visit 00), a physical examination will be performed by a study clinician licensed to make medical diagnoses and listed on the Form FDA 1572 as the site PI or sub-investigator. On Day 1 (Visit 01) prior to the first study vaccination and at follow-up visits after the first study vaccination, a targeted physical examination may be performed by a study clinician licensed to make medical diagnoses and listed on the Form FDA 1572 as the site PI or sub-investigator, if indicated based on subject's interim medical history.

Vital signs (oral temperature, pulse, and BP) will be collected at each study visit. Vital signs assessed on Day 1 prior to the first study vaccination will be considered as baseline. Subjects must not eat or drink anything hot or cold within 10 minutes prior to taking oral temperature.

Height and weight will be collected on the screening visit to determine BMI.

Pre-administration reactogenicity assessments will be performed prior to each study vaccination to establish baseline, then the study vaccination will be given.

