8.1.1 Adverse Events (AEs)

AE means any untoward medical occurrence associated with the use of an intervention in humans, whether or not considered intervention-related (21 CFR 312.32 (a)). In a patient or clinical investigation subject administered a pharmaceutical product regardless of its causal relationship to the study treatment. The FDA defines an AE as any untoward medical occurrence associated with the use of a drug in humans, whether or not considered drug related.

An AE can therefore be any unfavorable and unintended sign (including an abnormal laboratory finding), symptom or disease temporarily associated with the use of a medicinal (investigational) product. The occurrence of an AE may come to the attention of study personnel during study

visits and interviews of a study recipient presenting for medical care, or upon review by a study monitor. AEs, including solicited injection site and systemic (subjective and quantitative) reactions, not meeting the protocol-defined criteria for SAEs will be recorded on the appropriate DCF and entered into the eCRF. Information to be collected for unsolicited non-serious AEs includes event description, date of onset, licensed study physician's assessment of severity and relationship to study product or alternate etiology (if not related to study product) (assessed only by those with the training and authority to make a diagnosis and listed on the Form FDA 1572 as the site PI or sub-investigator), date of resolution, seriousness, and outcome. AEs occurring during the trial collection and reporting period will be documented appropriately regardless of relationship to study product. AEs will be followed through resolution.

Any medical condition that is present at the time that the subject is screened will be considered as baseline and not reported as an AE. However, if the severity of any pre-existing medical condition increases, it should be recorded as an AE.

If an event meets both the criteria of a study endpoint and an AE, the event will be reported either as a study endpoint or as an AE (not both).

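### The binary solicited-reaction analysis does not use the pre-dose baseline that the protocol requires, so unchanged background symptoms can raise the reported proportions and cannot lower them

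*Protocol*

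**What the plan says.** Section 7.1 (Clinical Evaluations) states: "Pre-administration reactogenicity assessments will be performed prior to each study vaccination to establish baseline". The same section lists what a reactogenicity assessment covers: local signs, and systemic symptoms such as fatigue, headache, arthralgia, nausea and diarrhea.

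Table 2 in section 3.2 makes solicited local and solicited systemic events two of the five primary endpoints. The systemic one reads "Occurrence of solicited systemic reactogenicity signs and symptoms for 7 days following each study vaccination".

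Section 10.5 gives two summaries of these endpoints. Solicited signs and symptoms "will be summarized by severity for each day post study vaccination (Days 1-8) and as the maximum severity over all 7 days". In addition, the worst response over follow-up is used for a binary variable, "dichotomizing into a binary variable (none versus mild, moderate, or severe"), and exact confidence intervals are given for the proportion of subjects with each symptom, any application-site symptom and any systemic symptom. Neither summary mentions the pre-dose grade. The same section does use baseline for another primary endpoint: "Clinical laboratory data will be summarized as change from baseline and by severity for each visit".

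Section 8.1.1 has a general baseline rule. A medical condition present at screening is baseline and is not an adverse event, but "if the severity of any pre-existing medical condition increases, it should be recorded as an AE".

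**The concern.** The protocol sets up a baseline for a primary endpoint at every dose and then states a counting rule that does not draw on it. Under that rule, a subject with mild fatigue just before the injection and the same mild fatigue afterwards counts as having a reaction.

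In a controlled trial a comparison arm would show this background. This trial is open-label and non-randomized with no control arm (section 3.1), so the single-group proportion is the estimate. The error also has one direction. The confidence interval conveys sampling error, but it does not show an upward shift from background symptoms, and that shift does not average out when groups are read together.

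**Working it through.** **1. Can a pre-dose symptom be present at vaccination?** Yes, within limits. Exclusion criterion 27 (section 5.1.3) bars acute illness within 72 hours but permits minor residual symptoms if the investigator judges that they will not interfere with assessing safety. Section 5.2.1 lets vaccination go ahead during a minor illness and gives diarrhea as an example. Diarrhea is a solicited event in section 8.1.1.1.

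**2. Does section 8.1.1 remove such symptoms from the count?** In part. It classes solicited reactions as adverse events ("AEs, including solicited injection site and systemic (subjective and quantitative) reactions, not meeting the protocol-defined criteria for SAEs"), so its baseline rule can reach them. But the rule is tied to screening, which falls on Day -30 to -1. It does not cover a symptom that starts between screening and Dose 1, or one that starts between doses. In the two-dose groups the second dose comes on Day 29, Day 57 or Days 85-130.

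**3. Size.** The protocol gives no background rate, so this is an assumption shown over a range. Let p be the true reaction rate. Let b be the share of subjects with a pre-dose symptom that persists unchanged and is not removed by section 8.1.1, independent of reacting.

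- Counted rate = p + b(1 − p)
- Excess = b(1 − p)

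| True rate p | b = 2% | b = 5% | b = 10% | b = 20% |
|---|---|---|---|---|
| 20% | 1.6 points | 4.0 | 8.0 | 16.0 |
| 50% | 1.0 | 2.5 | 5.0 | 10.0 |
| 90% | 0.2 | 0.5 | 1.0 | 2.0 |

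Example: p = 20% and b = 10% give 0.20 + 0.10 × 0.80 = 0.28, an excess of 8 points. In a group of 10 that is 0.8 of a subject. The range at p = 20% is 0.16 to 1.6 subjects.

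**4. If the vaccine caused no reactions.** The chance of counting at least one reactor among 10 is 1 − (1 − b)^10. This is the calculation behind Table 4, which gives 65.1% and 89.3% for n = 10 at event rates of 10% and 20%. Both reproduce: 1 − 0.90^10 = 65.1% and 1 − 0.80^10 = 89.3%. At b = 2% and 5% the chance is 18.3% and 40.1%.

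**5. Scale against sampling error.** The exact 95% interval for 2 of 10 is 2.5% to 55.6%. Within one group, sampling error is larger than any shift in the table.

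**6. Where the effect falls.** Injection-site symptoms are unlikely to be present before the injection. The solicited-event triggers in sections 8.1.6 and 8.5.1 count Grade 3 events, so mild background symptoms hardly bear on them.

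**The case against.** The strongest reply is that this belongs in the SAP, and that section 10.5 is silent on the pre-dose grade without saying it will be ignored. It is true that the SAP could settle the point. But section 10.5 names the SAP where it leaves room for it (missing data, descriptive statistics, geometric means), and the sentence on dichotomization has no such clause. As written, it is a stated rule.

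Second, the endpoint is worded as occurrence after vaccination, and an any-grade count estimates exactly that. In a first-in-human study, over-counting is the cautious error. This stands. The count misleads only if it is read as vaccine-caused, and that is a reason to keep it. The binary analysis is also additional to daily and maximum severity, so grade detail is not lost.

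Third, eligibility limits the problem. Besides the acute-illness criterion, inclusion criterion 4 (section 5.1.1) keeps out conditions that would affect the safety assessment, and allows chronic medication only where it does not compromise assessment of reactogenicity. This stands too, and narrows the gap without closing it.

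A reader might go further and infer that a subject with unchanged chronic arthralgia is counted as a reactor at every dose. Section 8.1.1 speaks against that, because a condition present at screening is baseline unless it worsens. A reader might also infer that the contrast between the 18-60 and >60 groups is biased. The documents give no background rates by age, and section 10.1 plans no hypothesis tests between schedule and dose groups.

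**Conclusion.** The point holds in a limited form. The protocol requires a reactogenicity baseline before each dose, and the binary solicited-event analysis does not use it. Without a control arm, and with minor pre-dose symptoms allowed, the effect on systemic proportions can only be upward.

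The documents do not support saying that the rates are in fact inflated, because no background rate is given. With an assumed pre-dose prevalence of 2% to 20%, independent of reaction and persisting unchanged, the excess is 1.6 to 16 points at a true rate of 20% and 0.2 to 2 points at 90%. It matters most where true reactogenicity is low. It is a cheap improvement to the primary safety summary and does not invalidate it.

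**What to change.** In section 10.5:

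- Keep the any-grade proportion as it is.
- Report beside it, with exact 95% confidence intervals, the proportion of subjects whose post-dose grade exceeds their own pre-administration grade for that symptom before that dose.
- Show pre-dose severity as a column next to Days 1-8 in the severity table.

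The sponsor should also confirm that the assessment required by section 7.1 is recorded per symptom in the eCRF. The vaccination-visit procedures (sections 6.2.1, 6.3.3, 6.4.5 and 6.6.6) and the schedules in Tables 6 to 9 name the post-vaccination evaluation but no pre-dose reactogenicity item.

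If the grade is recorded, the cost is one derived variable and one table column. The drawback is that a true reaction that only matches the pre-dose grade is missed by the baseline-adjusted proportion. It stays in the any-grade count, which is why both should be shown. No escalation or halting rule changes.
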